## 5.2 Exclusion criteria

Patients meeting **any** of the following criteria are **not** eligible for inclusion in this study. No additional exclusions may be applied by the investigator, in order to ensure that the study population will be representative of all eligible patients.

1. Mixed *Plasmodium* infections as per light microscopy results
2. Signs and symptoms of severe malaria according to [WHO 2015](#) (see [Section 16.4](#))
3. Significant, non-plasmodial co-infections including tuberculosis
4. Patients with concurrent febrile illnesses (e.g., typhoid fever, known or suspected COVID19)
5. Known relevant liver disease e.g. chronic hepatitis, cirrhosis, compensated or decompensated, history of hepatitis B or C, hepatitis B or A vaccination in last 3 months, known gallbladder or bile duct disease, acute or chronic pancreatitis
6. Major congenital defects
7. Any confirmed or suspected immunosuppressive or immunodeficient condition, including human immunodeficiency virus (HIV) infection or family history of congenital or hereditary immunodeficiency
8. Immunosuppressive therapy (steroids, immune modulators or immune suppressors) within 3 months prior to recruitment. (For corticosteroids, this will mean prednisone, or equivalent,  $\geq 0.5$  mg/kg/day. Inhaled and topical steroids are allowed)
9. Repeated vomiting (defined as more than 3 times in the 24 hours prior to inclusion in the study) or severe diarrhea (defined as more than 3 watery stools in the 24 hours prior to inclusion in the study)
10. Active duodenal ulcer, ulcerative colitis, Crohn's disease, chronic (i.e.,  $> 2$  weeks) use of non-steroidal anti-inflammatory drugs (NSAIDs)
11. Clinically relevant abnormalities of electrolyte balance which require correction, e.g., hypokalemia, hypocalcemia or hypomagnesemia
12. Anemia (hemoglobin level  $< 7$  g/dL)
13. Any surgical or medical condition which might significantly alter the absorption, distribution, metabolism, or excretion of drugs (e.g., HIV patients on ART therapy or TB patients on treatment), or which may jeopardize the patient in case of participation in the

study. The investigator should make this determination in consideration of the patient's medical history and/or clinical or laboratory evidence of any of the following:

- $AST/ALT > 3 \times$  the upper limit of normal range (ULN), regardless of the level of total bilirubin
  - $AST/ALT > 1.5$  and  $\leq 2 \times$  ULN and total bilirubin is  $> ULN$

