**Table 8-5 Local laboratory evaluations**

Test Category	Test Name
Hematology	Hemoglobin, hematocrit (packed-cell volume - PCV), platelets, white blood cell (WBC) count with differential (as much as possible, neutrophil, lymphocyte and eosinophils counts will be performed while basophils and monocytes can be aggregated as 'other'). Red blood cell count (RBC), reticulocyte count and haptoglobin levels will be performed in case of significant hemoglobin drop > 2g/dL or hemoglobin levels ≤ 5g/dL (will be optional depending on site equipment).
Chemistry	
Routine blood chemistry testing will be performed according to the visit schedule in order to monitor the general medical condition of the patient.
 
This includes: Glucose, creatinine (serum), transaminases (ALT/Serum glutamic pyruvic transaminase (SGPT) and AST/Serum glutamic oxaloacetic transaminase (SGOT)), serum-γ-glutamyl transferase (GGT), Total and direct bilirubin, Alkaline Phosphatase (ALP), Blood Urea Nitrogen (BUN), prothrombin time International Normalized Ratio (INR), sodium, potassium, magnesium, calcium, chloride, total protein and albumin.
 
Thyroid stimulating hormone (TSH) and free thyroxine T4 are tested at screening, Day 15 and at study completion only.
 
At screening, results of the thyroid test are not mandatory for eligibility into the study.

Urinalysis	Dipstick measurements for specific gravity, protein, glucose and hematuria. Microscopy will be performed and urine sediment will be assessed in case of an abnormal dipstick test.

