2.8.2 Laboratory data

Descriptive statistics will be generated for all clinical laboratory tests performed (actual values and changes from baseline) for three groups of laboratory tests (hematology, clinical chemistry and urinalysis) by laboratory test, visit and treatment group. Maximum change from baseline during study will also be reported. Change from baseline will only be summarized for patients with both baseline and post baseline values and will be calculated as:

$$\text{change from baseline} = \text{post baseline value} - \text{baseline value}$$

The following laboratory parameters will be analyzed for hematology test group: hemoglobin, platelets, white blood cell count, Reticulocytes, Haptoglobin, hematocrit, red blood cell (RBC) count, lymphocytes, lymphocytes (%), monocytes, monocytes (%), eosinophils eosinophils (%), neutrophils, neutrophils(%) , basophils, and basophils (%) .

The following laboratory parameters will be analyzed for Biochemistry test group: creatinine, total bilirubin (TBL), direct bilirubin, alanine aminotransferase (ALT), aspartate aminotransferase (AST), alkaline phosphatase (ALP), glucose, blood urea nitrogen (BUN). Sodium, potassium, calcium, creatinine, uric acid, gamma glutamyltransferase (GGT), magnesium, chloride, and total protein, albumin, INR, Thyroid Stimulating hormone (TSH), Thyroxine Free T4.

Change from baseline will only be analyzed for Hemoglobin, RBC, platelets, TBIL, ALT, AST.

Box plots for hematology and biochemistry parameters will be provided using normalized values, by dividing a value by its upper normal limit. Normalized values are used in the box plots since lab units and normal ranges could vary according to each site and also according to a certain age group. All lab values outside the normal ranges (High/Low) will be highlighted. The lab parameters without the normal reference ranges will be excluded from this plot.

Summary with frequency and percentage of patients with liver related events as defined in [Table 2-1](#) will be provided by treatment:

Table 2-1 Liver-related events

Parameter	Criterion
ALT	>3xULN; >5xULN; >8xULN; >10xULN; > 20xULN
AST	>3xULN; >5xULN; >8xULN >10xULN; >20xULN
ALT or AST	>3xULN; >5xULN; >8xULN >10xULN; >20xULN
ALT or AST and TBL	ALT or AST > 3 × ULN and TBL > 2 × ULN ALT or AST > 5 × ULN and TBL > 2 × ULN ALT or AST > 10 × ULN and TBL > 2 × ULN
TBL	>1.5xULN, >2xULN, >3xULN
ALP	>2xULN, >3xULN
ALP & TBL	ALP >3xULN & TBL >2xULN

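### SAP 2.8.2 summarises red cell count, reticulocytes and haptoglobin as routine tests, and red cell count as change from baseline, but the protocol measures them only when haemoglobin falls or is very low

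*SAP*

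**What the plan says.** Protocol Table 8-5 gives the routine haematology panel as "Hemoglobin, hematocrit (packed-cell volume - PCV), platelets, white blood cell (WBC) count with differential". A separate sentence covers the other three tests: "Red blood cell count (RBC), reticulocyte count and haptoglobin levels will be performed in case of significant hemoglobin drop > 2g/dL". The same sentence adds a second trigger, haemoglobin at or below 5 g/dL, and says that the tests "will be optional depending on site equipment".

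SAP section 2.8.2 makes no such distinction. Its haematology list runs "hemoglobin, platelets, white blood cell count, Reticulocytes, Haptoglobin, hematocrit, red blood cell (RBC) count" and continues with the differential. All listed tests get descriptive statistics for each visit and arm, and box plots are planned for haematology parameters. On change from baseline it states: "Change from baseline will only be analyzed for Hemoglobin, RBC, platelets, TBIL, ALT, AST". It also states: "Change from baseline will only be summarized for patients with both baseline and post baseline values". Nowhere does the SAP say that RBC, reticulocytes and haptoglobin are conditional tests.

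**The concern.** The SAP plans an analysis that the protocol's data collection does not support. RBC is one of only six tests chosen for change from baseline, yet the protocol provides no RBC value to serve as the baseline.

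For all three tests, the patients with a result are those whose haemoglobin has already fallen after randomisation. Treatment may affect who falls into that group. A by-arm mean within it is not a comparison of the randomised arms, although it would appear beside rows that are. The number that does compare the arms is how many patients in each had the fall, and the SAP does not tabulate it.

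**Working it through.** The plan states no figure to reproduce. The check sets the sections side by side and adds simple counts.

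**1. Can a baseline RBC arise under the protocol?** SAP section 2.1.1 defines baseline as the last value before the first dose. Protocol Tables 8-1 to 8-3 schedule one haematology sample before dosing, at screening; the next is at 24 h.
- Drop trigger (more than 2 g/dL): this needs an earlier haemoglobin value, and the schedule provides none before screening.
- Level trigger (5 g/dL or lower): protocol section 5.2 excludes haemoglobin below 7 g/dL, so an eligible patient is at least 7 − 5 = 2 g/dL above it at screening.

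Neither trigger can be met at the screening sample by an eligible patient. Planned baseline RBC values: 0. Since the SAP requires both a baseline and a post-baseline value, the number evaluable for RBC change under the protocol as written is also 0.

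**2. Who contributes post-baseline values?** The first trigger is a fall of more than 2 g/dL. The second requires going from 7 g/dL or higher to 5 g/dL or lower, a fall of at least 2 g/dL. Both therefore select on a haemoglobin fall after screening, and site equipment selects further. One other source exists: protocol section 6.2.3 requires a full blood count on the first day of rescue medication. Its components are not listed, it is post-baseline, and it is conditional on rescue.

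**3. How many patients could that be?** Arm sizes follow from the planned 1:1 randomisation: Cohort 1, 140/2 = 70; Cohort 2, 80/2 = 40; pooled, 220/2 = 110. The documents give no rate for the trigger, so the shares below are assumptions. Patients per arm = share × arm size.

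| Assumed share triggered | Cohort 1 (70) | Cohort 2 (40) | Pooled (110) |
|---|---|---|---|
| 2% | 1.4 | 0.8 | 2.2 |
| 5% | 3.5 | 2.0 | 5.5 |
| 10% | 7.0 | 4.0 | 11.0 |
| 20% | 14.0 | 8.0 | 22.0 |

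For each assumed share, these are ceilings on the number tested through the triggers over the whole follow-up. Any single visit would have no more, and sites without the equipment lower them further.

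**4. Is the trigger itself counted by arm?** SAP section 2.8.2 has threshold tables for liver tests and a listing for renal changes, but nothing for a haemoglobin fall of more than 2 g/dL or a level of 5 g/dL or lower. SAP section 5.5 grades laboratory values by CTCAE from the observed value, and does not provide for counting the fall. The shift tables in protocol section 12.5.2 use low, normal and high categories. None of these gives the count.

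**The case against.** The case on the other side is substantial, and most of it stands as a limit on impact.

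**Red-cell safety is covered elsewhere.** Haemoglobin is a routine test. The SAP analyses it by visit and arm as actual value, change from baseline and maximum change. Protocol section 12.5.2 adds shift tables to the worst post-treatment value, SAP section 5.5 adds CTCAE grading, and adverse events are tabulated by arm. A reader might infer that the red-cell safety comparison is lost or misleading. It is not; only the rows for the three conditional tests are affected.

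**RBC values may exist.** Safety tests are run in local laboratories. The SAP's change log shows that the restriction to six tests was added on 24 June 2024 after a dry run, which may mean that RBC values were seen. The documents do not say so. A reader might infer that the RBC change table is certain to be empty. That is what the protocol as written implies, but it is not an established fact about the data. If only some sites report RBC, the table describes a site-selected subset, and the SAP should say so.

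**Safeguards exist.** Continuous summaries show n, a change is calculated only where both values exist, and all laboratory data are listed. These prevent a false calculation. They do not make the by-arm means comparable.

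**The masking cannot be quantified from the documents.** A reader might truncate haemoglobin change at the trigger, average it by arm, and conclude that most of a true difference would be hidden. That calculation averages the same variable that defines the selection, and it needs means and SDs that the documents do not give. The SAP does not restrict haemoglobin to triggered patients, and reticulocytes and haptoglobin are different variables, so no such percentage carries over to them.

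**Conclusion.** The mismatch holds as written. Protocol Table 8-5 makes RBC, reticulocytes and haptoglobin conditional and optional by site equipment, while SAP 2.8.2 summarises them as routine tests and names RBC for change from baseline. With no baseline RBC planned, that change table would be empty or filled only from sites that report RBC anyway. The by-arm summaries of all three tests would describe patients selected on a post-baseline haemoglobin fall. The conclusion assumes that sites follow Table 8-5 and the haemoglobin exclusion; it does not depend on the assumed trigger shares.

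Severity is minor. The tables are descriptive and carry no hypothesis test, the primary analysis is unaffected, and the main red-cell assessment rests on haemoglobin in unselected patients. What is missing is a by-arm count of the fall that the protocol itself calls significant.

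**What to change.** First establish whether RBC was collected routinely, including at screening. If it was, document that and keep RBC in the change-from-baseline list. If not, amend SAP section 2.8.2 as follows:

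- Remove RBC from the change-from-baseline list.
- Replace the by-visit, by-arm summaries and box plots of RBC, reticulocytes and haptoglobin with a listing.
- Report, by cohort and arm, the number and percent of Safety-set patients with a haemoglobin fall of more than 2 g/dL from baseline or a level of 5 g/dL or lower, and the number of those who were tested.

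The cost is SAP wording and one small table built mainly from haemoglobin data already collected. The listing draws on laboratory listings that the protocol already plans. The downside is that three summary rows become a listing.

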2.8.3 Other safety data

2.8.3.1 ECG and cardiac imaging data

Average triplicate ECG measurements will be used for the summary.

The following quantitative variables will be summarized: heart rate, RR interval, PR interval, QRS interval, QT interval, QTcF (QT interval corrected for heart rate according to Fredericia) and QTcB (QT interval corrected for heart rate according to Bazett) for each timepoint and maximum post baseline value.

Descriptive summary statistics for the change from baseline for each post-baseline visit will be performed by ECG parameters and treatment group.

To assess the dynamics of QTc, HR and body temperature, patients with notable QT, HR and fever (≥ 37.5 °C, axillary equivalent) by timepoint will be provided. Notable criteria is provided below.

To assess the temporal correlations, mean change of QTcF over time, mean change of ECG HR over time, mean change of temperature over time, and PK concentration of KAF156 and lumefantrine over time will be plotted with all panels aligned on the x-axis (Time after dosing).

Post treatment max QTcF/QTcB increase from baseline will be calculated for each patient and 2-sided confidence intervals for the difference between the 2 treatment groups will be calculated based on two sample t-test using the 80% confidence level for the run-in cohort.

Post treatment QTcF/QTcB increase from baseline at common post-baseline timepoints (48H, Day 8, and Day 43) will be calculated for each patient and 2-sided confidence intervals for the difference between the 2 treatment groups will be calculated based on two sample t-test using the 90% confidence level for Cohorts 1 and 2.

QTc will be summarized categorically by computing the number and percentage of patients at each time point and at the maximum post baseline value with following:

- QT, QTcF, or QTcB
 - > 450 and \leq 480 ms
 - > 480 and \leq 500 ms
 - > 500 ms
 - Increase from Baseline of \geq 30 ms to < 60ms
 - Increase from Baseline of \geq 60 ms
- HR for age <18 years
 - > 90th percentile defined in [Table 2-2](#)
 - < 10th percentile defined in [Table 2-2](#)
- PR
 - Increase from baseline >25% and to a value > 200 ms
 - New value of > 200 ms
- QRS
 - Increase from baseline >25% and to a value > 120 ms
 - > 120 ms

Table 2-2 Heart rate cut-offs (beats/minute) based on centile charts

Age Range#	10 th percentile	90 th percentile
Birth	107	148
0 – <3m	123	164
3 – <6m	120	159
6 – <9m	114	152
9 – <12m	109	145
12 – <18m	103	140
18 – <24m	98	135
2 – <3y	92	128

Age Range#	10 th percentile	90 th percentile
3 – <4y	86	123
4 – <6y	81	117
6 – <8y	74	111
8 – <12y	67	103
12 – <15y	62	96
15 – <18y	58	92

Age ranges given in years (y) and months (m). “Birth” refers to the immediate neonatal period.

Reference: Lancet. 2011 March 19; 377(9770): 1011–1018. doi:10.1016/S0140-6736(10)62226-X.

Analysis will also be performed on all parameters by age categories (6 months to < 2 yrs, 2 to <6 yrs, 6 to <12 yrs, 12 to <18 yrs).

A line plot by patient (Spaghetti plot) will be provided by visit and treatment group.

A listing of all newly occurring or worsening abnormalities as compared with baseline will be provided, as well as a by-patient listing of all quantitative ECG parameters.

For DMC review meetings, following additional analysis will be provided;

- QRS - Increase from baseline >25% and (80≤ QRS≤100 ms) and Increase >25% and (100< QRS≤120 ms)
- Heart rate - <50 bpm, 51-60 bpm, 61-80 bpm, 81-100 bpm, and >100 bpm

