 For both KAF156/LUM-SDF and Coartem®, the PK sample at 24 h and 48 h should be collected prior to the drug administration.

[REDACTED]

 Body height will be measured at Study End in Cohort 2 only

 For KAF156/LUM-SDF the ECG at 24 h and 48 h and for Coartem at 48 should be performed prior to drug administration.

 Blood samples to be collected before administration of study treatment.

 To be done before administration of comparator only (Coartem®).

 Based on the outcomes of the Run-in cohort and study CKAF156A2202, laboratory evaluations done (Table 8-5) and the frequency of blood draws may be reduced.

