### 10.2.4 Cardiac Safety Monitoring

Although QTc extensions and bradycardia are often associated with acute malaria disease and subsequent recovery (fast reduction of fever and heart rate), QTc extensions and bradycardia are also seen as potential side-effects of many anti-malarials. Lumefantrine as part of Coartem®, has shown only modest increase of QTc in a dedicated TQT study, and extensive post-marketing surveillance has not shown signs of cardiotoxicity. ECG results from the previous study CKAF156A2202 where the combination of KAF156 and LUM-SDF was evaluated in acute malaria patients  $\geq 12$  years, did not show clinically relevant QTcF extensions and/or bradycardia following treatment. There was however a mild trend towards higher QTcF change from baseline with increasing exposures. Clinical relevance is unknown.

To ensure patient safety in this study and to fully characterize the cardiovascular safety of the investigational drug, a standardized process for identification, monitoring and evaluation of cardiac events by ECG is followed.

The following categories of notable ECG changes will be assessed during the course of the study (irrespective of whether classified/reported as (S)AE):

- QTcF increase from pretreatment baseline  $\geq 60\text{ ms}$
- QTcF  $> 500\text{ ms}$

Resting heart rate:

- HR (ECG) < 50/min with > 25% decrease from pretreatment baseline or
- HR (ECG) < 50/min associated with symptoms

Cardiac rhythm:

- Any cardiac arrhythmia associated with hemodynamical compromise
- Sustained ventricular tachycardia  $\geq$  30 sec, or ventricular fibrillation

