## **12-lead ECG:**

PR, QRS, QT, QTcF, QTcB, and RR intervals will be obtained from 12-lead ECGs for each patient during the study. ECG data will be read and interpreted (centrally).

Categorical Analysis of QT/QTc interval data based on the number of patients meeting or exceeding predefined limits in terms of absolute QT/QTc intervals or changes from baseline will be presented. In addition, a listing of these patients will be produced (by cohort and treatment group). Post treatment max QTc increase from baseline will be calculated for each patient and 2-sided confidence intervals for the difference between the 2 treatment groups will be calculated using the 80% confidence level for Run-in Cohort and the first 24 patients in Cohort 2 for Data Review checks and the 90% confidence level for all patients in each cohort at the final analysis.

All ECG data will be listed by cohort, treatment group, patient and visit/time, abnormalities will be flagged. Summary statistics will be provided by cohort, treatment group, and visit/time.

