			Changed the time to event/censoring from Day 41 to Day 43 in tail of KM plots	Section 2.1.1
			In the definition of uncorrected ACPR, deleted 'new infection' in the last bullet point; In the definition of PCR-corrected ACPR, added 'new infection' at the definition '□The patient is not classified as a non-responder at Day X and the malaria blood film result at Day X is missing and not followed by a subsequent negative result/new infection'.	Section 2.1.1.2
			In the definition of corrected ACPR and uncorrected ACPR, add a patient who take non-study antimalaria medications during the treatment period is considered as non-responder .	
			In the definition of corrected ACPR, add that if the patient has parasite cleared by Day 7 but has negative PCR prior	

Date	Time point	Reason for update	Outcome for update	Section and title impacted (Current)
			to Day X, the response is considered as missing/undetermined.	
			In PK analysis set, added two PK analysis subsets with different food compliance conditions for run-in cohorts and cohort 1 and cohort 2	Section 2.2
			For PCT and FCT censoring, added 'If the study medication is vomited in the same date as the use of antimalarial medication, the last vomiting time on the study medication date is imputed as time of antimalarial medication. Otherwise, the antimalarial medication time can be imputed using the middle day time (12:00).'	Section 2.7.2.4
			Changed the condition of clearance of initial infection from Day 15 to Day 7.	Section 2.7.2.5
			Included cohort 1 and cohort 2 separately for the treatment difference evaluation using a log-rank test	Section 2.7.2
			Changed the condition of clearance of initial infection from Day 15 to Day 7.	Section 2.7.2.6
			Added "Change from baseline will only be analyzed for Hemoglobin, RBC, platelets, TBIL, ALT, AST."	Section 2.8.2

Date	Time point	Reason for update	Outcome for update	Section and title impacted (Current)
			For Post treatment QTcF/QTcB increase from baseline for cohort 1 and cohort 2, it will only be analyzed at common post-baseline timepoints (48H, Day 8, and Day 43)	Section 2.8.3
			Lower limit of the Day 29 visit is changed from Day 25 to Day 27	Section 5.1.4
			In Table 5-6, Added three more time points 51 h, 54h, 68 h for ECG and PK sampling	Section 5.1.4
			Added more prohibited medications, in particular related to Liver enzymes (ALT/AST) elevation and QTc prolongation	Section 5.3

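### In Cohorts 1 and 2 the by-arm QTc categories at the post-baseline maximum set 7 or 9 ECGs against 4, so they are not comparable, and the shared-time interval that avoids this bias is insensitive to a peak effect.

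*SAP*

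**What the plan says.** Protocol 12.5.2 (12-lead ECG) planned the between-arm comparison on each patient's largest change: "Post treatment max QTc increase from baseline will be calculated for each patient and 2-sided confidence intervals for the difference" between the two groups, using "the 90% confidence level for all patients in each cohort at the final analysis". SAP 2.8.3.1 keeps the maximum for the Run-in Cohort. For Cohorts 1 and 2 it substitutes a 90% interval at three times: "Post treatment QTcF/QTcB increase from baseline at common post-baseline timepoints (48H, Day 8, and Day 43) will be calculated for each patient". The SAP change log shows that this was deliberate.

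The categorical analysis was not changed in the same way: "QTc will be summarized categorically by computing the number and percentage of patients at each time point and at the maximum post baseline value". The categories include QTc above 500 ms and increases of 30 to under 60 ms and of 60 ms or more. No caution about unequal ECG counts is attached.

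The ECG schedules differ by arm (Protocol Tables 8-2 and 8-3). On the timing of the 48 h ECG, the Table 8-3 footnote (3-day regimen) says: "For KAF156/LUM-SDF the ECG at 24 h and 48 h and for Coartem at 48 should be performed prior to drug administration".

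SAP Section 4 reports no change to protocol-specified analyses. SAP 5.7.3 still describes an interval for the maximum increase without limiting it to the Run-in Cohort.

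**The concern.** A maximum over more readings is larger than a maximum over fewer, even when the underlying values are the same. A by-arm table of maxima built on 7 or 9 ECGs against 4 therefore shows an excess for KAF156/LUM-SDF that has nothing to do with the drug. The SAP took this imbalance out of the confidence interval but left it in the table beside it.

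The interval has the opposite limitation. Its three times are the only ones the arms share, and none is soon after a dose. Protocol 10.2.4 says of the earlier combination study: "There was however a mild trend towards higher QTcF change from baseline with increasing exposures". A reader could take a narrow interval around zero as covering the time of highest exposure, which it does not. Protocol 10.2.4 also notes that QTc and heart rate move with recovery from malaria, so the control arm matters for interpretation. One by-arm output can thus suggest a false excess, while the other cannot address the peak.

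**Working it through.** **The plan's own QTc figure.** The only one is for the Run-in Cohort (Protocol 12.8.2): 80% power to exclude a 20 ms increase with 10 per group, SD 20 ms and a two-sided 80% interval. The noncentrality is 20 / (20 × √(2/10)) = 2.236 with 18 degrees of freedom and one-sided alpha 0.10, which gives 81.7%. The figure reproduces. No QTc power or precision is stated for Cohorts 1 and 2.

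**ECG counts after baseline.**

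| Arm | Treatment period | Follow-up | Total |
|---|---|---|---|
| KAF156/LUM-SDF, 2-day | 24, 27, 30, 48, 72 h | Day 8, Day 43 | 7 |
| KAF156/LUM-SDF, 3-day | 24, 27, 30, 48, 51, 54, 72 h | Day 8, Day 43 | 9 |
| Coartem | 48, 68 h | Day 8, Day 43 | 4 |

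For the 3-day schedule, Day 8 and Day 43 are taken from SAP 2.8.3.1, because the follow-up ECG rows of Table 8-3 were not in the text available to me. The SAP points to the 3-day regimen: section 2.2 defines food compliance in these cohorts over three dosing days, and Table 5-6 has ECG windows at 51 and 54 h.

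**Where the shared times fall.** Coartem is given at 0, 8, 24, 36, 48 and 60 h (Protocol 6.7.2).
- 48 h, Coartem: pre-dose, 48 − 36 = 12 h after the previous dose.
- 48 h, KAF156/LUM-SDF: 48 − 24 = 24 h after the previous dose. It is pre-dose in the 3-day regimen; in the 2-day regimen no further dose follows.
- Day 8 (168 h), Coartem: 168 − 60 = 108 h after the last dose.
- Day 8, KAF156/LUM-SDF: 168 − 48 = 120 h (3-day) or 168 − 24 = 144 h (2-day).

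The ECGs soon after a dose (27, 30, 51 and 54 h for KAF156/LUM-SDF; 68 h for Coartem) enter no between-arm interval.

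**Size of the artefact when the arms are identical.** Let the change at each time be a patient effect plus independent error, with total SD s, within-patient correlation ρ and zero mean at every time. These values are assumptions; the documents do not give them. The expected maximum over k readings is c_k × s × √(1 − ρ), where c_k is the expected maximum of k independent standard normals: c_4 = 1.029, c_7 = 1.352, c_9 = 1.485.

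At s = 20 ms and ρ = 0.5:
- 9 against 4: (1.485 − 1.029) × 20 × 0.707 = 6.4 ms.
- 7 against 4: (1.352 − 1.029) × 20 × 0.707 = 4.6 ms.
- Maximum of at least 30 ms, by simulation: 29.0% (9 ECGs), 25.6% (7), 18.5% (4). Numerical integration agrees to within 0.1 point.
- Maximum of at least 60 ms: 1.0% (9) against 0.5% (4).

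With 110 randomised per arm, the 30 ms category would hold 0.290 × 110 ≈ 32 patients against 0.185 × 110 ≈ 20.

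Over s = 15 to 20 ms and ρ = 0.3 to 0.9, the excess in the mean maximum runs from 0.456 × 15 × 0.316 = 2.2 ms to 0.456 × 20 × 0.837 = 7.6 ms (9 against 4), and from 1.5 to 5.4 ms (7 against 4). The share at or above 30 ms is 1.25 to 1.9 times (9 against 4) or 1.2 to 1.6 times (7 against 4) as large.

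**Non-flat means, same profile in both arms** (9 against 4, s = 20, ρ = 0.5). If the mean rises linearly to 20 ms by Day 8 and stays there, the excess is 2.3 ms and the 30 ms category is 55% against 50%. If it is 10 ms to 72 h and then zero, the excess is about 9 ms. The sign is the same in both cases.

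**After matching.** With the maximum limited to the three shared times, each arm has 3 scheduled ECGs, and the artefact from unequal counts is zero by construction.

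**The protocol's interval.** With 70 per arm, s = 20, ρ = 0.5 and identical arms, a 90% interval for the difference in maxima would lie wholly above zero with probability about 0.73 (9 against 4) or 0.49 (7 against 4); the nominal value is 0.05. Moving away from it was justified.

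**The case against.** The strongest reply is that this is descriptive safety reporting. ECG abnormality is part of a secondary safety endpoint, and Cohorts 1 and 2 have no QTc hypothesis, margin or power. The near-peak data are not discarded: SAP 2.8.3.1 summarises change from baseline by arm at every post-baseline visit, gives the categories at each time point, plots QTcF alongside drug concentrations, and provides patient-level plots and listings. The maximum-based table carries no test, and its bias runs against the investigational arm, so it cannot hide harm. The size of the artefact rests on assumed SD, correlation and mean profile. All of this stands, and it limits the point to how two outputs are built and labelled.

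Three stronger readings are tempting, and the documents do not support them.
- A reader might infer that the interval uses only washed-out times. For Day 8 this is contradicted: Protocol 12.8.2 makes lumefantrine at 168 h the key PK parameter, and Protocol 4.2 links Day 8 concentrations to response.
- A reader might infer that 48 h is pre-dose in both arms. That holds only under the 3-day schedule.
- A reader might infer that the ECG objective is answered wrongly in both directions. The by-time summaries remain, and no QTc time course is given, so any loss of sensitivity at the peak cannot be quantified.

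The reply does not rescue the table of maxima. It is presented by arm without a caution, although the SAP had already moved the interval to shared times.

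**Conclusion.** The point holds in a limited form. In Cohorts 1 and 2 the QTc categories at the post-baseline maximum are not comparable between arms, because KAF156/LUM-SDF has 7 or 9 ECGs and Coartem 4. The extra ECGs alone raise the KAF156/LUM-SDF proportions. The direction is not in doubt. The illustrated size for an increase of at least 30 ms (29.0% or 25.6% against 18.5%) rests on SD 20 ms, correlation 0.5 and a zero mean, and it changes with each of these.

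The shared-time interval is free of that bias but includes no ECG soon after a dose, so it is insensitive to a peak effect and should not be read as excluding one. By how much cannot be computed from the documents.

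Separately, SAP Section 4 is wrong to report no change, because the maximum-based interval of Protocol 12.5.2 was replaced for these cohorts.

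**What to change.** In SAP 2.8.3.1, for Cohorts 1 and 2:
- Base the between-arm categorical maximum on the ECG times both arms share: 48 h, Day 8 and Day 43.
- Show the all-ECG maximum for each arm separately, labelled as not comparable between arms because of unequal ECG counts.
- State that the common-time-point interval does not address a peak effect, and refer the reader to the by-time summaries.

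In SAP Section 4, list the replacement of the Protocol 12.5.2 maximum-based interval, and align SAP 5.7.3 so that the interval for the maximum applies only where it is still planned.

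A comparison of the ECGs after the last dose could be added, but only as optional and exploratory. It would set KAF156/LUM-SDF at 54 h (3-day) or 30 h (2-day), 6 h after the last dose, against Coartem at 68 h, 8 h after the last dose. The arms then differ by 68 − 54 = 14 h or 68 − 30 = 38 h in time since first dose, so recovery from malaria confounds the difference.

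The cost is one extra table and some wording; no new ECGs are needed. The matched maximum leaves out the near-peak ECGs, which remain in the per-time-point summaries.
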